# **6.1.** Screening Period

The Screening Phase begins when the ICF is signed. Screening evaluations will be performed for all subjects to determine study eligibility. These evaluations must be completed within 28 days of first dosing unless noted otherwise below.

Waivers to the protocol will not be granted during the conduct of this trial, under any circumstances.

Except for pregnancy tests, ECGs and urinalysis, all safety-related laboratory assessments will be performed centrally; however, tests that may result in dose interruption and/or modification may also be performed locally to allow for treatment-related decisions during subject visits. All results from local laboratories used in treatment decisions or AE reporting must be entered as an unscheduled visit into the electronic case report form (eCRF).

The following will be performed at screening as specified in Table 4 after informed consent has been obtained:

- Interactive Response Technology (IRT) registration
  - Note: Subject may be enrolled in the IRT up to 3 days prior to initiating study treatment on Cycle 1 Day 1 (C1D1)
- Complete medical history (all relevant medical conditions diagnosed/occurring prior to screening should also be included)
- Demographics (age, sex, race, and if allowed by local regulations, ethnicity, and date of birth, will be collected in the eCRF and/or IRT system)
- Prior disease history (if available the date of initial diagnosis, staging at time of diagnosis [Appendix D], cytogenetics at diagnosis to be collected)
- Prior disease therapies (including surgery, radiation, systemic or any other therapy for the subject's disease)
- Prior and concomitant medication evaluation (including those taken ≤ 28 days before the date that the ICF was signed, except for those taken for disease)
- Prior and concomitant procedures evaluation (including all procedures occurring ≤ 28 days before the date that the ICF was signed)
- Adverse events
- Physical examination, including assessment for potential venous thromboembolism events (VTEs) (can be source documented only)
- Forced expiratory volume test (subjects with or suspected to have chronic obstructive pulmonary disease [COPD])

- Vital signs (including blood pressure, temperature, and heart rate)
- Height and weight
- 12-lead ECG (performed and reviewed locally)
- Hepatitis panel
- HIV-1 antibody test

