#### 7.2.4.1. Dose Modification Instructions for Durvalumab

Refer to Appendix E for detailed instructions for DURVA dose modifications and toxicity management.

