## 8.2. Prohibited Concomitant Medications and Procedures

The following medications are prohibited (except for the outlined exceptions) during the study. The Sponsor must be notified if a subject receives any of these during the study.

- 1. Subjects who fail ANC, hemoglobin or platelet eligibility criteria at Screening should not be retested for the study after being treated with growth factors or platelet/RBC transfusion.
- 2. Any investigational anticancer therapy.
- 3. Any concurrent chemotherapy, radiotherapy (except palliative radiotherapy), immunotherapy, biologic or hormonal therapy for cancer treatment.
- 4. Immunosuppressive medications including, but not limited to systemic corticosteroids at doses exceeding 10 mg/day of prednisone or equivalent, methotrexate, azathioprine, and tumor necrosis factor alpha (TNF-α) blockers. The following exceptions apply:
  - a. Pre and post infusion medications as outlined in Table 6 and Table 7 for the management of infusion-related reactions.
  - b. Use of immunosuppressive medications in subjects with contrast allergies (eg, CT scan contrast hypersensitivity) is acceptable.
  - c. Use of inhaled, topical, or intranasal corticosteroids or local steroid injections (eg, intra-articular injection) is permitted.

- d. Temporary uses of corticosteroids for concurrent illnesses (eg, food allergies) are acceptable upon discussion and agreement with the Medical Monitor.
- 5. Live attenuated vaccines during the study through 30 days after the last dose of DURVA.
- 6. Herbal and natural remedies are to be avoided.
- 7. Egg cell and sperm donation

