# Appendix E: Durvalumab Treatment Modification and Toxicity Management Guidelines

Note: The toxicity management guidelines in Appendix E-1, E-2, and E-3 prepared by the Sponsor are to assist the investigator in the exercise of his/her clinical judgment in treating these types of toxicities and should be applied to management of adverse events related to study treatment and not ANY adverse event.

Appendix E-1: Durvalumab Treatment Modification and Toxicity Management Guidelines for Immune-related Adverse Events

	Immune-Mediated Reaction	ons
	Dose Modifications	Toxicity Management
Immune-related Adverse Events (Overall Management For toxicities not noted below)	Drug administration modifications of study drug/study regimen will be made to manage potential immune-related AEs based on severity of treatment-emergent toxicities graded per NCI CTCAE v4.03.  In addition to the criteria for permanent discontinuation of study drug/regimen based on CTC grade/severity (table below), permanently discontinue study drug/study regimen for the following conditions:  • Inability to reduce corticosteroid to a dose of ≤10 mg of prednisone per day (or equivalent) within 12 weeks after last	It is recommended that management of irAEs follow the guidelines presented in this table  - Patients should be thoroughly evaluated to rule out any alternative etiology (eg, disease progression, concomitant medications, infections, etc.)  - In the absence of a clear alternative etiology, all events should be considered potentially immune related.  - Symptomatic and topical therapy should be considered for low-grade (Grade 1 or 2, unless otherwise specified) events
	
 
dose of study drug/regimen
 
Recurrence of a previously experienced Grade 3 treatment-related AE following resumption of dosing.
 
Grade 1 No dose modification
 
Grade 2 Hold study drug/study regimen dose until Grade 2 resolution to ≤ Grade 1
 
If toxicity worsens then treat as Grade 3 or
 
	
 
For persistent (greater than 3 to 5 days) low-grade (Grade 2) or severe (Grade ≥3) events promptly start prednisone PO 1-2mg/kg/day PO or IV equivalent
 
If symptoms recur or worsen during corticosteroid tapering 28 days of taper), increase the corticosteroid dose (prednisone dose [eg, up to 2-4mg/kg/day PO or IV equivalent]) until stabilization or improvement of symptoms, then resume corticosteroid tapering at a slower rate (≥ 28 days of taper)
 

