	Grade 1 (Asymptomatic, clinical or diagnostic observations only, intervention not indicated)	No dose modification required. However, consider holding study drug/study regimen dosing as clinically appropriate and during diagnostic work-up for other etiologies	For Grade 1 (Radiographic Changes Only)  - Monitor and closely follow up in 2-4 days for clinical symptoms, pulse oximetry (resting and exertion) and laboratory work-up and then as clinically indicated  - Consider pulmonary and infectious disease consult

	Immune-Mediated Reaction	ons
	Dose Modifications	Toxicity Management
Grade 2 (Symptomatic, medical intervention indicated, limiting instrumental ADL)	
 
Hold study drug/study regimen dose until Grade 2 resolution to ≤ Grade 1
 
If toxicity worsens then treat as Grade 3 or Grade 4
 
If toxicity improves to ≤ Grade 1 then the decision to reinitiate study drug/regimen will be based upon treating physician's clinical judgment and after completion of steroid taper.
 
	
 
For Grade 2 (Mild to Moderate New Symptoms)
 
Monitor symptoms daily and consider hospitalization
 
Promptly start systemic steroids (eg, prednisone 1-2mg/kg/day PO or IV equivalent)
 
Reimaging as clinically indicated
 
If no improvement within 3-5 days, additional workup should be considered and prompt treatment with IV methylprednisolone 2-4mg/kg/day started
 
If still no improvement within 3-5 days despite IV methylprednisone at 2-4/g/kg/day, promptly start immunosuppressive therapy such as TNF inhibitors (eg, infliximab at 5 mg/kg every 2 weeks). Caution: Important to rule out sepsis and refer to infliximab label for general guidance before using infliximab
 
Once improving, gradually taper steroids over ≥ 28 days and consider prophylactic antibiotics, antifungal or anti PCP treatment (refer to current NCCN guidelines for treatment of cancer-related infections (Category 2B recommendation)
 
Consider pulmonary and infectious disease consult
 
Consider as necessary discussing with study physician
 

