	Grade 2 diarrhea (stool frequency of	Hold study drug/study regimen until resolution to ≤ Grade 1	For Grade 2 diarrhea:  - Consider symptomatic treatment including hydration,

EDMS Doc. Number: CCI

	Immune-Mediated Reactio	ns
	Dose Modifications	Toxicity Management
4-6 over baseline per day)	
 
If toxicity worsens then treat as Grade 3 or Grade 4
 
If toxicity improves to ≤ Grade 1 then study drug/study regimen can be resumed after completion of steroid taper
 
	electrolyte replacement, dietary changes (eg, American Dietetic Association colitis diet), and loperamide and/or budesonide  Promptly start prednisone 1 to 2 mg/kg/day PO or IV equivalent  If event is not responsive within 3-5 days or worsens despite prednisone at 1-2 mg/kg/day PO or IV equivalent, GI consult should be obtained for consideration of further workup such as imaging and/or colonoscopy to confirm colitis and rule out perforation, and prompt treatment with IV methylprednisolone 2-4mg/kg/day started.  If still no improvement within 3-5 days despite 2-4mg/kg IV methylprednisolone, promptly start immunosuppressives such as (infliximab at 5 mg/kg once every 2 weeks³). Caution: Important to rule out bowel perforation and refer to infliximab label for general guidance before using infliximab  Consult study physician if no resolution to ≤ Grade 1 in 3-4 days  Once improving, gradually taper steroids over ≥28 days and consider prophylactic antibiotics, antifungals and anti PCP treatment (please refer to current NCCN guidelines for treatment of cancer-related infections [Category 2B recommendation])

<sup>3 ASCO Educational Book 2015 Michael Postow MD "Managing Immune Checkpoint Blocking Antibody Side Effects.

Immune-Mediated Reactions			
	Dose Modifications		Toxicity Management
	Grade 3 or 4 diarrhea  (Grade 3: stool frequency of ≥7 over baseline per day;  Grade 4: life threatening consequences)	Permanently discontinue study drug/study regimen	For Grade 3 or 4 diarrhea:  - Promptly initiate empiric IV methylprednisolone 2 to 4 mg/kg/day or equivalent  - Monitor stool frequency and volume and maintain hydration  - Urgent GI consult and imaging and/or colonoscopy as appropriate  - If still no improvement within 3-5 days of IV methylprednisolone 2 to 4mg/kg/day or equivalent, promptly start further immunosuppressives (eg, infliximab at 5 mg/kg once every 2 weeks).  - Caution: Ensure GI consult to rule out bowel

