Grade 3 (AST or ALT > 20 times ULN and/or TB > 3.0-times ULN	-Hold study drug/study regimen dose until	For Grade 3 or 4 AST or ALT and/or TB elevation:  - Promptly initiate empiric IV methylprednisolone at 1 to 4 mg/kg/day or equivalent  - If still no improvement within 3-5 days despite 1 to 4 mg/kg/day methylprednisolone IV or equivalent,	

<sup>4 ASCO Educational Book 2015 "Managing Immune Checkpoint Blocking Antibody Side Effects", by Michael Postow MD.

Immune-Mediated Reactions			ns
		Dose Modifications	Toxicity Management
	Grade 4 (AST or ALT > 20 times ULN and/or TB > 10 times ULN)	baseline within 14 days and after completion with steroid taper.  Permanently discontinue study drug/study regimen if the elevations do not downgrade to ≤ Grade 1 or baseline within 14 days  For elevations in transaminases > 8 × ULN or elevations in bilirubin > 5 × ULN, discontinue study drug/study regimen  Permanently discontinue study drug/study regimen for any case meeting Hy's law criteria (AST and/or ALT > 3x ULN + bilirubin > 2x ULN without initial findings of cholestasis (ie, elevated alkaline P04) and in the absence of any alternative causeiv Permanently discontinue study drug/study regimen	
 
promptly start treatment with immunosuppressive therapy (mycophenolate mofetil) Discuss with study physician if mycophenolate is not available. Infliximab should NOT be used.
 
Hepatology consult, abdominal workup, and imaging as appropriate.
 
Once improving, gradually taper steroids over ≥28 days and consider prophylactic antibiotics, antifungals and anti PCP treatment (please refer to current NCCN guidelines for treatment of cancer-related infections [Category 2B recommendation])
 

Nephritis or Renal Dysfunction (Elevated Serum Creatinine)	Grade of Elevated Serum Creatinine (CTCAE version 4.03)  Any Grade	General Guidance	
 
Consult with Nephrologist
 
Monitor for signs and symptoms that may be related to changes in renal function (eg, routine urinalysis, elevated serum BUN and creatinine, decreased creatinine clearance, electrolyte imbalance, decrease in urine output, proteinuria, etc.)
 
Patients should be thoroughly evaluated to rule out any alternative etiology (eg, disease progression, infections etc.)
 
Steroids should be considered in the absence of clear alternative etiology even for low grade events (Grade 2), in order to prevent potential progression to higher grade event
 

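### Protocol Section 8.2 item 4 has no exception for treating durvalumab immune-related events, so read literally it bars the infliximab and mycophenolate that Appendix E calls for

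*Protocol*

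**What the plan says.** Section 8.2 of the protocol lists medications that may not be given during the study apart from the exceptions it sets out. Item 4 bars "Immunosuppressive medications including, but not limited to systemic corticosteroids at doses exceeding 10 mg/day of prednisone or equivalent", and goes on to name methotrexate, azathioprine and TNF-alpha blockers. Four exceptions follow:

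- a: the daratumumab pre- and post-infusion medications;
- b: immunosuppressants for contrast allergy;
- c: inhaled, topical, intranasal or locally injected steroids;
- d: "Temporary uses of corticosteroids for concurrent illnesses (eg, food allergies) are acceptable upon discussion and agreement with the Medical Monitor".

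Appendix E-1 sets out how durvalumab immune-related events are to be treated. For persistent Grade 2 or for severe events, its overall guidance is to "promptly start prednisone PO 1-2mg/kg/day PO or IV equivalent". When steroids fail, it escalates:

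- Grade 2 pneumonitis: "promptly start immunosuppressive therapy such as TNF inhibitors (eg, infliximab at 5 mg/kg every 2 weeks";
- Grade 3 or 4 diarrhea: "promptly start further immunosuppressives (eg, infliximab at 5 mg/kg once every 2 weeks";
- Grade 3 or 4 hepatitis: "promptly start treatment with immunosuppressive therapy (mycophenolate mofetil".

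Section 7.2.4.1 sends the investigator there: "Refer to Appendix E for detailed instructions for DURVA dose modifications and toxicity management". Section 6.1 states: "Waivers to the protocol will not be granted during the conduct of this trial, under any circumstances".

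**The concern.** The two parts of the protocol give opposite answers for the same patient. Appendix E-1 tells the investigator to give a TNF inhibitor or mycophenolate, while Section 8.2 puts both in a prohibited class and offers no exception that fits. For systemic steroids, the nearest exception adds an agreement step where Appendix E wants treatment begun at once.

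The events are foreseeable. Colitis, pneumonitis and hepatitis are all on the list of adverse events of special interest in SAP Section 11.2, and Appendix E-1 provides for life-threatening grades. A site that works from the prohibited-medication list alone could hold back rescue treatment or wait for agreement. It is also unclear whether a site that follows Appendix E has committed a protocol deviation. SAP Section 7 leaves that to a company procedure that is not in the documents.

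**Working it through.** The protocol gives no figure to reproduce. The check is a comparison of texts, plus a short dose calculation for steroids.

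**Step 1. Do any of the exceptions apply?** Infliximab belongs to a class that item 4 names. Mycophenolate is not named, but item 4 is open-ended and mycophenolate is an immunosuppressant. Exception a is tied to the infusion medications of Tables 6 and 7, b to contrast allergy, c to local steroid routes, and d to corticosteroids. So 0 of 4 exceptions cover either drug for an immune-related event. Sections 8.1 (permitted) and 8.3 (required) add no such permission.

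**Step 2. How many Appendix E-1 instructions conflict with item 4?**

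| Event | Grades with an instruction | Drug | Count |
|---|---|---|---|
| Pneumonitis/ILD | 2; 3 or 4 | Infliximab (TNF inhibitor) | 2 |
| Diarrhea/enterocolitis | 2; 3 or 4 | Infliximab | 2 |
| Hepatitis | 2; 3 or 4 | Mycophenolate mofetil | 2 |

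2 + 2 + 2 = 6 for these two drugs. Appendix E-1 also calls for additional immunosuppression, with IVIG as its example, in neurotoxicity of Grade 2 and of Grade 3 or 4. On the same open-ended reading of item 4 that adds 2, giving 8, so six is a lower bound. Separately, the overall guidance says TNF inhibitors should be considered when systemic steroids fail.

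**Step 3. Do the Appendix E steroid doses exceed the limit?** The limit is 10 mg/day of prednisone or equivalent. The lowest starting prednisone dose is 1 mg/kg/day, which equals the limit at 10 / 1 = 10 kg. Every adult weighs more, so every adult exceeds it.

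The documents give no weight distribution. I assume 50-100 kg to show the range:

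- Prednisone 1-2 mg/kg/day: 50 × 1 = 50 mg/day up to 100 × 2 = 200 mg/day, or 5 to 20 times the limit.
- Methylprednisolone 1-4 mg/kg/day, converted by Table 7 (4 mg equals 5 mg prednisone, factor 5/4 = 1.25): 50 × 1 × 1.25 = 62.5 mg/day up to 100 × 4 × 1.25 = 500 mg/day, or 6.25 to 50 times the limit.

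Exceeding the limit depends only on the 10 kg threshold, not on the assumed weights.

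**Step 4. Does another sentence settle the conflict?** Section 7.2.4.1 and the opening of Section 8 point to Appendix E for durvalumab toxicity. Section 10.7 expects steroids and immunosuppressants to be used for events of special interest. These show intent. None is written as an exception to Section 8.2, and no sentence says that Appendix E prevails.

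**Step 5. Who is affected?** The prohibition runs for the whole study. After Grade 2 pneumonitis or diarrhea resolves, study drug may be resumed, so the conflict is not confined to patients already off treatment. Three uses are unaffected: topical steroid for rash (exception c), steroid replacement at 10 mg/day or less, and isolated hypothyroidism managed by hormone replacement.

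**The case against.** The strongest reply is that the intent is plain and sits close by. Section 8 opens by saying that medication may be needed for side effects of trial treatment and refers to Appendix E. A specific toxicity instruction can reasonably be read as controlling a general list. Section 8.2 itself foresees that listed drugs may be given, since it asks that the Sponsor be notified. Nothing shows that a clinician facing refractory colitis would withhold infliximab.

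The intent is accepted, and it tells us which text to correct. But Section 8.2 confines its exceptions to those it lists, and a duty to notify is not a permission. Clinicians would probably treat anyway; they should not have to depart from the protocol's literal text to do so.

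Other points reduce the weight of parts of the argument:

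- Appendix E says it assists clinical judgment, so calling its content directions is slightly strong. Its wording is nonetheless imperative, and Section 7.2.4.1 treats it as instructions. If it is only guidance, it is less able to override an express prohibition.
- Section 10.1 counts a new intercurrent illness as an adverse event, so exception d might be read to cover an immune-related event. That makes the steroid part arguable, but it leaves the agreement step in place and does nothing for infliximab or mycophenolate.
- Grade 3 or 4 pneumonitis and diarrhea and Grade 4 hepatitis require permanent discontinuation, so the practical tension is greatest for patients who may resume.
- The no-waiver sentence sits in the screening section. Its wording covers the whole trial, but the finding does not depend on it.
- Deviations are summarized and listed, and the full analysis, safety and efficacy evaluable populations in SAP Section 5.2 are not defined by them. The deviation question is therefore one of reporting, not of analysis.

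**Conclusion.** The concern holds. As written, Section 8.2 item 4 contradicts the toxicity instructions in Appendix E-1. At least six grade-level instructions call for infliximab or mycophenolate with no applicable exception, and eight do if IVIG is counted as an immunosuppressant under item 4. The steroid doses exceed the limit for every adult, and the only arguable route to them is an exception that requires agreement first.

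The conclusion rests on the literal text. It does not assume that treatment would in fact be withheld, and the documents give no event rate from which to estimate how many subjects would be affected. This should be corrected for patient safety and clear conduct. It has no bearing on sample size, power or the efficacy analyses.

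**What to change.** Add an exception e to Section 8.2 item 4, along these lines:

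> Systemic corticosteroids and other immunosuppressants, including TNF inhibitors and mycophenolate, given to manage study-treatment toxicity in line with Appendix E are permitted and need no prior agreement from the Medical Monitor.

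The general term also covers IVIG. Keep the existing requirement to notify the Sponsor, and add one sentence stating that such use is not a protocol deviation.

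The cost is one exception and one sentence in a protocol amendment, with the ethics review that Section 13.5 requires. Sample size, power and the planned analyses do not change.

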# **8.3.** Required Concomitant Medications and Procedures

- **Infusion reaction prophylaxis:** Pre infusion and post infusion medications for infusion reaction prophylaxis will be given as detailed in Table 6.
- Antiviral prophylaxis: All subjects must initiate antiviral prophylaxis to prevent herpes zoster reactivation within 1 week of starting DARA and continue for 3 months following last dose of DARA.
  - Acceptable antiviral therapy includes acyclovir (eg, 400 mg given orally 3 times a day, or 800 mg given orally 2 times a day or per institutional standards), famciclovir (eg, 125 mg given orally, twice a day or per institutional standards), or valacyclovir (eg, 500 mg given orally, twice a day or per institutional standards), initiated within 1 week after the start of study drug.

### 9. STATISTICAL CONSIDERATIONS

#### 9.1. Overview

This is a single-arm, multicenter, Phase 2 study to evaluate the efficacy and safety of the combination regimen of DARA plus DURVA in subjects with RRMM who have progressed while on last MM treatment (DARA-containing regimen)

This section defines the subject populations for the statistical data analyses, the justifications of sample size, and the methodologies that will be used for the efficacy and safety analyses. All statistical analyses specified in the protocol will be conducted using SAS Version 9.2 or higher unless otherwise specified.

# 9.2. Study Population Definitions

For the purpose of statistical analyses and data presentation, the study populations are defined as follows:

## 9.2.1. Full Analysis Set Population

The full analysis set population (FAS) will include all enrolled subjects. The primary efficacy analyses will be performed on the FAS population.

